The endpoint of interest is accuracy as measured by the Accuracy root-mean-square (A_{rms}) difference between the Device Under Test (DUT) and the Reference Respiratory Rate as counted by EtCO₂ scored waveform (Ref) for all stable respiratory periods where

Clinimark [name]	TITLE: Respiratory Rate Verification Study – Gabi SmartCare Gabi Band Study ID# PR 2022-495 Principal Investigator: [name] Site ID # 001	DOCUMENT NUMBER PR# 2022-495 SHEET 15 of 28	REV 1
--	--	---	----------

$$A_{rms} = \sqrt{\frac{\sum(DUT - Ref)^2}{n}}$$

Mean bias will also be generated:

$$Bias = \frac{1}{n} \sum_{i=1}^n (DUT_i - Ref_i)$$

Acceptance Criteria: Passing requires an A_{rms} of ≤ 3.0 cpm.

Sample Size Justification

This study will utilize a sample size of 20 participants with 7 to 11 usable data points per participant, providing ≥ 200 data points over the specified breath per minute range.

Success for this study is defined as $A_{rms} \leq 3$ cpm. The A_{rms} statistic measures accuracy of a device under test (DUT) when compared to a reference device (REF) over a range of values. Accuracy, measured by the A_{rms} statistic, can be affected by both random and systematic components of error. Here we estimate power to obtain an $A_{rms} \leq 3$ cpm for this study through simulation using parameters estimated from two preliminary studies conducted previously by Clinimark. Respiratory rate study 1 composed of 894 data points from 18 study participants. respiratory rate study 2 composed of 913 data points from 20 study participants. Both studies had respiratory rate targets of 5, 10, 15, 20, 25, 30, 35, 40 and 45 breaths per minute. The A_{rms} statistics are 2.8 cpm and 1.2 cpm for Study 1 and Study 2 respectively. For more information about the results and standard respiratory rate metrics please refer to 'Summary of Respiratory Rate Data and Results from Clinimark Studies' dated May 1, 2019. These preliminary data contain the features of real data, such as within participant correlation that is present due to repeated measurements on the same study participants. Note this sample size was conducted on studies with adult populations where paced breathing can be used to get a range of repository rates. Participants in this study will breathe at their natural rate.

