Repeated measures within participants is a common practice in the pulse oximetry field but is known to potentially lead to within participant correlation, which is accounted for in these power estimates. Linear mixed models (LMM) were used to estimate parameters for each study in order to take into account repeated measures within participants. DUT was treated as the dependent variable. Participant was treated as a random effect, and REF was treated as a fixed effect. Parameter estimates from the mixed model were used as parameter estimates for simulations. The variance between participants in the mixed model results were used to model within individual correlation. Residual variance was used to model variance within participants. The estimated effect of REF was modeled as slope. The simulation model also incorporated mean bias. The simulation model was as follows:

$$DUT_{ij} = m \times REF_{ij} + B + \sigma^2_{between} + \sigma^2_{within}$$

- m = slope; B = mean bias; σ^2 = variance;
- i = measure; j = individual

Simulations were performed for the studies with a range of 10 to 38 individuals and 1 to 5 measurements at each respiratory rate target of 5, 10, 15, 20, 25, 30, 35, 40 and 45 breaths per minute, for a total of 145 different study size combinations. For each study size, 10,000 simulations were performed and the percentage of simulated studies that passed was taken as the estimate of power for that study size combination. Parameter estimates from study 1 resulted in the most conservative power estimates, and are as follows:

$m: 0.97039$

$B: -0.08434$

$\sigma^2_{between}: 0.4724$

$\sigma^2_{within}: 7.04$

Based on parameter estimates from study 1 the following combinations study sizes would have $>80\%$ to obtain $A_{rms} \leq 3$ cpm: (Participants x measurements) 27x9, 16x18, 11x27, 10x36. A study design with 30 participants and 18 measurements per participant has $>80\%$ power to obtain $A_{rms} \leq 3$ cpm given the expectation that the device

Clinimark [name]	TITLE: Respiratory Rate Verification Study – Gabi SmartCare Gabi Band Study ID# PR 2022-495 Principal Investigator: [name] Site ID # 001	DOCUMENT NUMBER PR# 2022-495 SHEET 16 of 28	REV 1
--	--	---	----------

performs the same as Study 1. Statistical modeling and simulations were performed using R (R 3.5.3 GUI El Capitan build, the R Foundation for Statistical Computing, 2016).

[figure not shown]

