## 1 Evaluation method

Accuracy is stated in terms of the root-mean-square (rms) difference between measured values ( $\hat{x}_i$ ) and reference values ( $x_i$ ), as given by

$$A_{\text{rms}} = \sqrt{\frac{\sum_{i=1}^n (\hat{x}_i - x_i)^2}{n}}$$

$A_{\text{rms}}$  must be below 3 cpm (cycles per minute) to meet the specification.

From a statistical perspective, this specification is achieved ("success") if the **one-sided 95% confidence interval** of  $A_{\text{rms}}$  lies below 3 cpm.

In case of repeated measures per subject, the above formula is modified as follows

$$A_{rms} = \sqrt{\frac{\sum_{i=1}^n \sum_{j=1}^m (\hat{x}_{ij} - x_{ij})^2}{nm}}$$

where  $i = 1, \dots, n$  indexes the subjects, and  $j = 1, \dots, m$  indexes the repeated measures within a subject.

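### The protocol's >80% power was simulated on an evenly paced adult 5–45/min grid for sample sizes this trial does not plan, and it should be restated for the planned size at natural breathing rates

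*Protocol*

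**What the plan says.** All of the following is in the Protocol, Sample Size Justification, unless another place is named.

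- **Pass rule** (Protocol, Endpoint / Comparator): "Passing requires an A_{rms} of ≤ 3.0 cpm". This is a rule on the point estimate, and the protocol's power figures use it.
- **Rates simulated:** "1 to 5 measurements at each respiratory rate target of 5, 10, 15, 20, 25, 30, 35, 40 and 45 breaths per minute".
- **Source of the parameters:** "Note this sample size was conducted on studies with adult populations where paced breathing can be used". The next sentence reads "Participants in this study will breathe at their natural rate".
- **Model:** "The estimated effect of REF was modeled as slope. The simulation model also incorporated mean bias". The printed values from Study 1 are m = 0.97039, B = -0.08434, between-participant variance 0.4724 and within-participant variance 7.04.
- **Claimed power:** above 80% for 27x9, 16x18, 11x27, 10x36 and 30x18, provided the device performs as in Study 1.
- **Planned size:** 20 participants with 7–11 usable points each. The Summary and the Objectives give a minimum of 23 participants.
- **Coverage:** the points are to be obtained "over the specified breath per minute range". Neither document specifies a range. The Procedure contains no pacing; it encourages quiet and marks quiet periods.

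**The concern.** A reader of the section would take it that this trial has more than 80% power. That figure belongs to another design in two respects. None of the listed participant-by-measurement combinations is the one planned, and the even spread of rates from 5 to 45/min was produced by pacing, which this trial does not use.

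The second point matters because the slope is below 1. Under the printed model the device reads progressively lower than the reference as the rate rises, so the chance of passing depends on which rates the children produce. The protocol discloses that breathing will be natural but does not carry this into any number. Two things are at stake: the sponsor's real chance of passing, and the range of rates over which a pass supports an accuracy claim.

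**Working it through.** **1. Model for the difference.** Let d = DUT − REF. With B as an intercept,

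d = (m − 1)·REF + B + b + e = −0.02961·REF − 0.08434 + b + e,

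where b ~ N(0, 0.4724) is the participant effect and e ~ N(0, 7.04) is the residual. A simulated trial passes if √(mean d²) ≤ 3.

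**2. Reproduce the stated power on the 5–45/min grid.**

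| Design | Power, B as intercept |
|---|---|
| 27x9 | 80–80.5% |
| 16x18 | 81% |
| 11x27 | 80–80.5% |
| 10x36 | 82% |
| 30x18 | 88% |

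All are at or above 80%, and the first four sit next to that boundary, so this is the protocol's calculation. With B as the mean bias at the grid centre of 25/min, d = −0.02961·(REF − 25) − 0.08434 + b + e. Then 27x9 gives 96.6%, which does not fit a list of designs that only just reach 80%.

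**3. Planned size on the same grid (B as intercept).** 20x9 gives about 77% and 23x9 about 78%. With rates drawn at random from the nine targets, 20x7 gives 75% and 20x11 gives 79%. Among the planned combinations only the top corner, 23x11, reaches about 80%.

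**4. Dependence on rate.** At a constant rate R,

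A_rms² = 0.4724 + 7.04 + (0.02961·R + 0.08434)² = 7.5124 + (0.02961·R + 0.08434)².

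Setting A_rms = 3 gives 9 − 7.5124 = 1.4876. Its root is 1.2197, and (1.2197 − 0.08434)/0.02961 = 38.3/min.

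Over the grid, the mean of REF is 25 and the mean of REF² is 791.67. The mean squared bias is therefore 0.02961²·791.67 + 2·0.02961·0.08434·25 + 0.08434² = 0.826, and A_rms = √(7.5124 + 0.826) = 2.89. A constant rate with the same mean squared bias is (√0.826 − 0.08434)/0.02961 ≈ 28/min. Below about 28/min power is higher than on the grid, and above it power is lower.

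**5. Power for 23x9 at natural rates.** The documents give no rates for these ages. I assumed normal rates with SD 6 between children and 3 within a child, so the rate variance is 36 + 9 = 45. This adds 0.02961²·45 = 0.039 to A_rms².

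| Mean rate (/min) | Expected A_rms, B as intercept | Power, B as intercept | Power, B centred at 25/min |
|---|---|---|---|
| 20 | 2.83 | 88% | 97% |
| 25 | 2.87 | 82% | 97% |
| 30 | 2.92 | 72% | 96% |
| 35 | 2.97 | 59–60% | 95% |
| 40 | 3.03 | 45% | 92% |
| 45 | 3.09 | 30% | 88% |

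Repeated runs differ by up to about one percentage point.

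**6. Which reading of B?** The text labels B as mean bias, and the centred reading gives a grid A_rms of √(7.5124 + 0.02961²·166.67 + 0.08434²) = 2.77, close to the 2.8 reported for Study 1. The intercept reading gives 2.89 but is the only one that reproduces the claimed power. The printed material does not settle the matter.

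**The case against.** The strongest case on the other side has four parts.

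- **The limitation is disclosed and the parameters are conservative.** The protocol says the source data came from adults and uses the less favourable of its two earlier studies. That is true, but disclosure does not turn the figure into one for this trial.
- **Low power is mainly the sponsor's risk.** It does not loosen the pass rule. That is also true, and it limits how serious the point is.
- **The SAP has its own paediatric calculation.** It uses no paced targets and no slope, and its success rule is stricter: the "one-sided 95% confidence interval" must lie below 3 cpm. For a bias up to 2 and variances up to 0.75 it needs 10–12 patients, fewer than the protocol plans. This calculation stands on its own assumptions. It does not repair the protocol's figure, which rests on another model, much larger within-participant variance and another pass rule.
- **The rate effect depends on B.** Under the centred reading it is small over 20–45/min. This stands, and it is why the rate-specific figures are conditional.

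A reader might go further and infer that the protocol's stated power drops below 80% above about 26/min and below 50% above about 38/min. The documents do not support that. The 26/min crossing belongs to sizes such as 20x9, which was below 80% on the grid already. At a constant rate the listed designs cross 80% at about 28/min, and 30x18 at 31/min. The 50% crossing is near 39/min, and 38.3/min is where expected A_rms reaches 3.0. All of these need B to be an intercept.

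**Conclusion.** The point holds in a limited form. The claim of more than 80% power describes an evenly paced 5–45/min grid at sizes this trial does not plan. On that grid the planned size at 9 points has about 77% (20 participants) or 78% (23 participants), a shortfall of two to three percentage points that does not depend on any assumption about children's rates. It does rest on B being an intercept.

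Beyond that, power is uncertain rather than shown to be low. For 23x9 and mean rates of 20–40/min it runs from about 88% down to 45% if B is an intercept, and from about 97% down to 92% if B is centred. These ranges rest on the assumed SDs of 6 and 3. A reader might infer that the trial is underpowered because young children breathe fast. The documents give no natural rates, so they support neither that inference nor its opposite. This should be corrected, but it does not prevent the acceptance rule from being applied.

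**What to change.** 1. State whether B is an intercept or the mean bias and, if it is the mean bias, the rate at which it is centred.
2. Rerun the existing simulation for the planned number of participants (20 or 23, once reconciled) with 7–11 points each. Use a natural-rate distribution for the planned age mix, labelled as an assumption and shown over a range. The age range has to be settled first, because the Protocol Overview gives 0–5 years and the eligibility criteria 0–12.
3. Replace the >80% statement with that result.
4. Delete the reference to a specified range of breathing rates, since none is specified.
5. State that the accuracy conclusion applies to the range of reference rates observed, and report that range.

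The cost is one simulation rerun and a few sentences. Enrolment and procedures need not change for this. The downside is that the stated power may be less favourable and the accuracy claim is confined to the observed rates.

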Clinimark [name]	TITLE: Respiratory Rate Verification Study – Gabi SmartCare Gabi Band Study ID# PR 2022-495 Principal Investigator: [name] Site ID # 001	DOCUMENT NUMBER PR# 2022-495 SHEET 27 of 28	REV 1
--	---	--	-----------------

Appendix B: Sample Waveform Scoring Form

Below is an example of the waveform scoring form. The reviewers counting the raw EtCO₂ waveform will be blinded to the results from the test device.

Respiratory Rate _____

Scorer Name _____ Date _____

Checked by _____

Date _____

Clinimark [name]	TITLE: Respiratory Rate Verification Study – Gabi SmartCare Gabi Band Study ID# PR 2022-495 Principal Investigator: [name] Site ID # 001	DOCUMENT NUMBER PR# 2022-495 SHEET 28 of 28	REV 1
---	--	--	------------------

## Context

⌚ Sample size calculation to validate respiratory rate (RR) accuracy by comparison of repeated paired readings from the test system and the reference system in a pediatric population: neonates (0 - 28 days); infants (28 days - 2 years); children (2 years - 5 years).

## 1 Evaluation method

Accuracy is stated in terms of the root-mean-square (rms) difference between measured values ( $\hat{x}_i$ ) and reference values ( $x_i$ ), as given by

$$A_{\text{rms}} = \sqrt{\frac{\sum_{i=1}^n (\hat{x}_i - x_i)^2}{n}}$$

$A_{\text{rms}}$  must be below 3 cpm (cycles per minute) to meet the specification.

From a statistical perspective, this specification is achieved ("success") if the **one-sided 95% confidence interval** of  $A_{\text{rms}}$  lies below 3 cpm.

In case of repeated measures per subject, the above formula is modified as follows

$$A_{rms} = \sqrt{\frac{\sum_{i=1}^n \sum_{j=1}^m (\hat{x}_{ij} - x_{ij})^2}{nm}}$$

where  $i = 1, \dots, n$  indexes the subjects, and  $j = 1, \dots, m$  indexes the repeated measures within a subject.

**This document provides information on the sample size requirement for such a study.**

## 2 Paragraph for the study protocol

### 4 paired readings per subject

Assuming that the mean of the absolute differences between measured values and reference values is  $\leq 2$  and that the between-subject and within-subject variances are  $\leq 0.75$ , a minimum sample size of 12 patients (resulting in 48 paired data points) was computed to achieve  $\geq 80\%$  power in demonstrating that  $A_{rms}$  is below 3 cpm, at the 95% confidence level.

### 10 paired readings per subject

Assuming that the mean of the absolute differences between measured values and reference values is  $\leq 2$  and that the between-subject and within-subject variances are  $\leq 0.75$ , a minimum sample size of 11 patients (resulting in 110 paired data points) was computed to achieve  $\geq 80\%$  power in demonstrating that  $A_{rms}$  is below 3 cpm, at the 95% confidence level.

### 20 paired readings per subject

Assuming that the mean of the absolute differences between measured values and reference values is  $\leq 2$  and that the between-subject and within-subject variances are  $\leq 0.75$ , a minimum sample size of 10 patients (resulting in 200 paired data points) was computed to achieve  $\geq 80\%$  power in demonstrating that  $A_{rms}$  is below 3 cpm, at the 95% confidence level.

## 3 Details

### Constructing the confidence interval of $A_{rms}$

A confidence interval of  $A_{rms}$  can be obtained by bootstrap. The resampling scheme must take the hierarchical nature of the data into account (repeated measures). The non-parametric bootstrap simply consists of randomly sampling

subjects with replacement (Davison and Hinkley (1997), Section 3.8). In its parametric version, resample data can be generated according to the classical linear random effects model:

$$d_{ij} = \mu_0 + b_i + \epsilon_{ij} \quad (d_{ij} = \hat{x}_{ij} - x_{ij})$$

with  $b_i \sim N(0, \sigma_b^2)$  and  $\epsilon_{ij} \sim N(0, \sigma_e^2)$ .

 Alternatively, the distributional properties of  $A_{rms}$  are studied in Ndikintum and Rao (2016) based on the above model, under balanced settings (e.g., no missing values). In particular, the expression of the variance of  $A_{rms}^2$  in that paper reveals that it is more beneficial to increase the number of patients rather than the number of replicates per patient. Bayesian estimation is yet another option.

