## Sample size calculation

The sample size is determined to reach  $\geq 80\%$  power, i.e. to reach a *probability of success* of  $\geq 80\%$ , using the bootstrap method.

The power of the study has been estimated from 1000 simulations in the following settings:

- The data are generated from the above model in order to reflect the hierarchical nature of the study data (Ndikintum and Rao (2016));
- The number of patients  $n$  varies between 5 and 20;
- The number of paired readings per subject  $m$  is set to 4, 10, and 20;
  - The total number of paired data points equals  $n \times m$ .
- The bias between the two methods ( $\mu_0$ ) varies between 0 and 2;
- The within-subject variability of the differences ( $\sigma_e^2$ ) varies between 0.5 and 1;
- The between-subject variability ( $\sigma_b^2$ ) is set equal to  $\sigma_e^2$ .
  - Worst-case scenario according to Ndikintum and Rao (2016).

The table below reports the value of the population accuracy,  $\sqrt{\sigma_e^2 + \sigma_b^2 + \mu_0^2}$ , for each scenario:

[figure not shown]
mu0	sig2e	sig2b	Arms
0.00	0.50	0.50	1.00
0.00	0.75	0.75	1.22
0.00	1.00	1.00	1.41
1.50	0.50	0.50	1.80

mu0	sig2e	sig2b	Arms
1.50	0.75	0.75	1.94
1.50	1.00	1.00	2.06
1.75	0.50	0.50	2.02
1.75	0.75	0.75	2.14
1.75	1.00	1.00	2.25
2.00	0.50	0.50	2.24
2.00	0.75	0.75	2.35
2.00	1.00	1.00	2.45

[figure not shown]

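### The SAP does not name its bootstrap limit, and at its 12, 11 or 10 subjects ordinary percentile limits pass a device with true A_rms of 3 about 8–11% of the time, not 5%

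*SAP*

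**What the plan says.** SAP section 1 sets the rule: "From a statistical perspective, this specification is achieved" when the upper one-sided 95% limit of A_rms falls under 3 cpm.

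SAP section 3, on constructing the interval, says a bootstrap can supply it and adds: "The resampling scheme must take the hierarchical nature of the data into account (repeated measures". It describes a non-parametric version that resamples whole subjects, then a second: "In its parametric version, resample data can be generated according to the classical linear random effects model". Published distribution theory for balanced data and Bayesian estimation are mentioned as further options.

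The sample size part of section 3 says power was obtained "using the bootstrap method", without saying which version. It continues: "The power of the study has been estimated from 1000 simulations in the following settings". The listed scenarios have a population A_rms from 1.00 to 2.45.

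SAP section 2 gives the results for 80% power at 95% confidence, with a difference of at most 2 and variances of at most 0.75:
- 4 readings: "a minimum sample size of 12 patients (resulting in 48 paired data points) was computed to achieve" this.
- 10 readings: "a minimum sample size of 11 patients (resulting in 110 paired data points) was computed to achieve" this.
- 20 readings: "a minimum sample size of 10 patients (resulting in 200 paired data points) was computed to achieve" this.

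The Protocol (Endpoint / Comparator) passes the device on a point estimate of A_rms of at most 3.0, with no confidence limit. Its Sample Size Justification speaks of 20 participants with 7 to 11 readings each, and its Objectives of at least 23.

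**The concern.** With 10 to 12 subjects, bootstrap limits of different types can differ enough to change pass into fail. Leaving the type open means the decision rule is not fully specified before data are seen.

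A bootstrap limit labelled 95% also need not cover 95% of the time in so few subjects. The between-subject variance is estimated on only 9 to 11 degrees of freedom, and a percentile limit makes no allowance for that uncertainty. The way to find out is to simulate a device exactly at the limit of 3 and count how often it passes. The SAP's grid does not reach that value. If coverage falls short, the confidence level attached to the stated sizes is not the one achieved.

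**Working it through.** **Inputs.** Limit 3 cpm, one-sided level 95% (SAP section 1). Model d_ij = μ0 + b_i + e_ij, with variances σ²b between and σ²e within subjects (SAP section 3). Sizing case μ0 = 2, σ²b = σ²e = 0.75 (SAP section 2, reading the stated mean difference as the bias μ0 of section 3). Readings m = 4, 10, 20.

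**Formulas.** Population A_rms = √(μ0² + σ²b + σ²e). In the sizing case this is √(4 + 0.75 + 0.75) = √5.5 = 2.35, as in the SAP table. The observed mean square is A² = (SSW + SSB)/(nm) + d̄², where
- SSW ~ σ²e · χ² on n(m−1) df,
- SSB ~ (σ²e + mσ²b) · χ² on n−1 df,
- d̄ ~ N(μ0, (σ²e + mσ²b)/(nm)).

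The parametric bootstrap redraws A² from these with estimated values put in (ANOVA/REML variances). The percentile limit is the 95th percentile of 1,000 draws, and the trial passes if that limit is below 9 on the squared scale.

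**Step 1: reproduce the stated sizes** (40,000 trials per cell, power at μ0 = 2, variances 0.75).

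| m | stated n | power at stated n | power at n−1 |
|---|---|---|---|
| 4 | 12 | 80.5% | 78.4% |
| 10 | 11 | 82.4% | 79.4% |
| 20 | 10 | 80.8% | 78.1% |

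The parametric percentile limit reproduces 12/11/10. So do a parametric bias-corrected and a parametric normal limit. The SAP's 1,000 simulations carry a standard error of √(0.8 × 0.2/1000) = 1.3 points, so the sizes cannot identify the method.

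**Step 2: false-pass rate at a true A_rms of 3.** Set μ0 = √(9 − σ²b − σ²e): √8 = 2.828 with variances 0.5, √7.5 = 2.739 with 0.75, √7 = 2.646 with 1.

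| limit (nominal 95%) | variances | 12×4 | 11×10 | 10×20 |
|---|---|---|---|---|
| parametric percentile | 0.5 | 8.2% | 8.3% | 7.9% |
| parametric percentile | 0.75 | 8.4% | 8.3% | 8.4% |
| parametric percentile | 1 | 9.2% | 8.7% | 8.8% |
| subject-resampling percentile | 0.75 | 10.5% | 10.4% | 10.9% |

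Repeat runs of the parametric limit at 0.75 gave 8.0% to 9.0%. The two other limits that match 12/11/10 give 8.1–8.6%. Maximum-likelihood variances raise the parametric percentile rate to 9.7–10.2%. If the excess error is variance rather than bias (μ0 = 2 with variances 2.5, or μ0 = 0 with variances 4.5; both sum to 9), the REML rate is 9.2–10.3%.

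Actual confidence is 100% minus these rates: about 91–92% for the parametric percentile limit and about 89–90% for subject resampling.

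**Step 3: power of better-calibrated limits at 12×4, 11×10, 10×20** (variances 0.75).

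| limit | false pass | power |
|---|---|---|
| studentised subject bootstrap, log mean square | 6.3%, 5.8%, 6.1% | 65.8%, 67.1%, 64.0% |
| parametric percentile, nominal 97% | 5.8%, 6.0%, 6.2% | 74.5%, 76.8%, 75.3% |
| parametric percentile, nominal 97.5% | 5.2%, 5.3%, 5.5% | 72.2%, 74.5%, 73.1% |

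The last two rows are tuned at one variance setting and are for illustration only.

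**Step 4: larger samples.** At 23 subjects with 9 readings (variances 0.75), false pass is about 7% for parametric percentile, about 8% for subject-resampling percentile and 5.4% for studentised, the last with 94% power.

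**Step 5: different variance split.** The Protocol's Sample Size Justification gives 0.4724 between and 7.04 within subjects (adults, paced breathing). With a constant bias assumed, μ0 = √(9 − 7.5124) = 1.22. At the SAP's sizes the parametric percentile limit then passes falsely 6.0–6.9% of the time and the studentised limit 6.3–6.8%, so these two barely differ. Subject-resampling percentile gives 11.1–11.9%.

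**The case against.** The strongest reply is that section 3 of the SAP is a menu in a sizing document, that the power figures reproduce, and that the Protocol adopts none of 12, 11 or 10. Its own numbers are 20 and at least 23, where the excess is about 2 to 3 points and power is ample. Its pass rule uses no confidence limit at all. The SAP's figures and most of its results table are not readable here, so a label naming the limit may exist. All of this stands and limits the consequence. It does not remove the gap: a plot label would not fix the rule for the final analysis, and no listed scenario tests a true A_rms of 3.

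A reader might infer three stronger things that the material does not support.
- That the SAP used a parametric percentile limit. The sizes fit it, but they fit other limits too.
- That correcting the coverage necessarily cuts power at 12/11/10 to the mid-60s. That holds for the studentised limit; a stricter parametric percentile limit keeps about 71–77%.
- That the Phase II minimum of 15 participants is too few if only they supply verification data. At 15 subjects with 9 readings the studentised limit has about 80% power and the stricter parametric limit about 85%, so any shortfall depends on the limit chosen.

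**Conclusion.** The point holds. The readable SAP names neither the bootstrap version nor the limit. Both versions it describes, taken with ordinary percentile limits, miss the stated 95% confidence at the stated sizes. False pass at a true A_rms of 3 is about 8–9% (parametric, variances 0.5 to 1) or about 10–11% (subject resampling), against a nominal 5%. The claim of 80% power is reproduced; the confidence level paired with it is not achieved.

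This rests on the SAP's normal random-effects model with equal between- and within-subject variances and equal readings per subject. The parametric excess is smaller under the Protocol's variance split (6.0–6.9%) and at 23 subjects with 9 readings (about 7%). It bears on the trial's conclusion only if the SAP's limit rule decides success. It should be corrected, but it does not by itself undermine a verification in 20 or more participants.

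**What to change.** 1. Reconcile SAP section 1 with the Protocol's Endpoint / Comparator section and state which rule decides success. The difference is large: at a true A_rms of 3 and the SAP's sizes, the point-estimate rule passes about 52% of the time.
2. If the limit rule governs, pre-specify one limit with better small-sample coverage that also handles 7 to 11 readings per participant. One example is a studentised subject bootstrap on the log mean square, with the standard error recomputed in each resample. Its false-pass rate is about 6%, not exactly 5%, at the SAP's sizes.
3. Add scenarios with a true A_rms of 3 and report the achieved false-pass rate.
4. Restate the power, or the minimum sizes, for the chosen limit and for the number of participants who will actually supply verification data. That number should allow for the Protocol's statement that developmental data are kept separate.

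The cost is SAP wording and a rerun of the simulation grid. The stated figure will look somewhat less favourable than 80% power at 10 to 12 subjects.
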